#### **5.2.2. Drinking Days**

A drinking day is one calendar day in which the subject reported any alcohol consumption (i.e.,  $> 0$  standard drinking units [SDUs]). A standard drink contains approximately 0.6 fluid ounces (oz) of pure alcohol. The data given by the subjects on amount and type of alcoholic beverage(s) consumed will be converted to SDUs. Standard drink unit definitions are provided in **Table 2**.

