**Table 2: Standard Drink Unit Definitions**

For Beer (~ 5% alcohol), the approximate number of SDUs in:

• 12 oz = 1.0

• 16 oz = 1.3

• 24 oz = 2.0

• 40 oz = 3.3

For malt liquor (~ 7% alcohol), the approximate number of SDUs in:

• 12 oz = 1.4

• 16 oz = 1.9

• 22 oz = 2.6

• 40 oz = 4.7

For table wine (~ 12% alcohol), the approximate number of SDUs in:

• 750 mL bottle = 25oz = 5.0

• 5 oz glass = 1.0

• 10 oz glass = 2.0

For 80 proof spirits (~ 40% alcohol), or hard liquor, the approximate number of SDUs in:

• 1.5 oz (mixed drink) = 1.0

• 16 oz (pint) = 8.5

• 25 oz (a fifth) = 17.0

• 1.75 L (59 oz) = 39.0

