### **5.2.3. Very Heavy and Heavy Drinking Day**

A very heavy drinking day is defined as 8 or more drinks per day for a woman, and 10 or more for men. A heavy drinking day is defined as a day with 5 or more drinks (SDUs) for males and 4 or more drinks (SDUs) for females.

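### SAP Table 2's pint row for 80-proof spirits (16 oz set to 8.5 SDU) contradicts the SAP's own standard-drink definition, which gives 10.7; volume and value must be reconciled

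*SAP*

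**What the plan says.** SAP Section 5.2.2 defines the unit: "A standard drink contains approximately 0.6 fluid ounces (oz) of pure alcohol". It then says: "The data given by the subjects on amount and type of alcoholic beverage(s) consumed will be converted to SDUs", and refers to Table 2 (Standard Drink Unit Definitions) for the values.

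The spirits block of Table 2 opens: "For 80 proof spirits (~ 40% alcohol), or hard liquor, the approximate number of SDUs in". It has four rows. Three read "1.5 oz (mixed drink) = 1.0", "25 oz (a fifth) = 17.0" and "1.75 L (59 oz) = 39.0". The fourth, the pint, sets 16 oz at 8.5.

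SDUs feed the thresholds in SAP Section 5.2.3: "A very heavy drinking day is defined as 8 or more drinks per day for a woman, and 10 or more for men", and "A heavy drinking day is defined as a day with 5 or more drinks (SDUs) for males and 4 or more drinks (SDUs) for females". They also feed weekly drinks, calculated to the tenth of an SDU (SAP Section 5.2.7), and the WHO risk level at 14 g per SDU (SAP Section 5.2.8).

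**The concern.** One row of the conversion table does not follow from the definition beside it or from its neighbours. Sixteen ounces of the same spirit score 10.7 if counted as 1.5 oz drinks and 8.5 if entered as a pint.

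The secondary drinking endpoints that use quantity or cut-points in SDU depend on this conversion. If the row is applied as printed, a subject's drinks per week, very-heavy days or WHO level can depend on how the amount was reported and not only on what was drunk.

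**Working it through.** **Inputs.** 0.6 oz of pure alcohol per SDU (SAP 5.2.2); about 40% alcohol for spirits and the row values (Table 2); very-heavy day at 10 or more SDU for men and 8 or more for women, heavy day at 5 and 4 (SAP 5.2.3); 14 g per SDU and the WHO bands (SAP 5.2.8).

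**Step 1: reproduce the table.** SDU = volume (oz) × alcohol fraction / 0.6.

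| Spirits volume | Table 2 | By the definition | Difference | SDU per oz in Table 2 | Implied for 16 oz |
|---|---|---|---|---|---|
| 1.5 oz | 1.0 | 1.5 × 0.40 / 0.6 = 1.00 | 0% | 0.667 | 10.67 |
| 16 oz | 8.5 | 16 × 0.40 / 0.6 = 10.67 | −20.3% | 0.531 | n/a |
| 25 oz | 17.0 | 25 × 0.40 / 0.6 = 16.67 | +2.0% | 0.680 | 10.88 |
| 59 oz | 39.0 | 59 × 0.40 / 0.6 = 39.33 | −0.8% | 0.661 | 10.58 |

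The eleven beer, malt liquor and wine rows were checked in the same way. All agree within 2.5%; the largest gap is 16 oz of beer, 1.3 against 16 × 0.05 / 0.6 = 1.33. So 14 of 15 rows reproduce and only the pint fails.

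**Step 2: what would make 8.5 right.** Volume: 8.5 × 0.6 / 0.40 = 12.75 oz. Strength at 16 oz: 8.5 × 0.6 / 16 = 0.319, about 32% alcohol. Also, 8.5 is exactly half of the 17.0 given for the 25 oz bottle. Table 2's wine block equates 25 oz with 750 mL, so half is 375 mL. A slip in the volume label is therefore plausible.

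**Step 3: size if the amount really is 16 oz.** 10.67 − 8.5 = 2.17 SDU per pint, and 2.17 / 10.67 = 20.3%. Against the other spirits rows the shortfall is 19.6% (10.58) to 21.9% (10.88).

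**Step 4: which endpoints move.** The drinking patterns below are illustrations.
- *Drinks per week, one pint a day:* 8.5 × 7 = 59.5 against 10.67 × 7 = 74.7. Drinks per drinking day: 8.5 against 10.7.
- *Very-heavy day, men, one pint and nothing else:* 8.5 is below 10; 10.67 is not. The status flips unless other drinks that day add at least 10 − 8.5 = 1.5 SDU. For women both values exceed 8, so nothing flips.
- *Heavy day, one full pint:* both values exceed 5 and 4, so nothing changes for either sex.
- *WHO level, a pint every second day:* 8.5 / 2 × 14 = 59.5 g/day against 10.67 / 2 × 14 = 74.7 g/day. For a man this is Medium (41 to 60) instead of High (61 to 100). For a woman it is High (41 to 60) instead of Very High (61 and above).
- *WHO level, a pint a day:* 119 against 149 g/day, Very High for both sexes either way.
- *WHO decrease:* a subject going from a pint a day at baseline to a pint every second day starts at Very High under both values. With 8.5, the man falls two levels and the woman one; with 10.67, the man falls one and the woman none. Using the same row at baseline does not cancel the error here.
- *Abstinence:* depends only on whether SDU exceeds 0, so it is unchanged.

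**The case against.** The table calls its values approximate. That does not cover a 20% gap when every other row agrees within 2.5%.

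Four objections do stand and limit the point:
- **Direction.** A reader might infer that the SAP under-counts pints by 20%. The documents do not settle this. If the container meant is about 12.75 oz, 8.5 is right for it and only the label is wrong.
- **Use of the row.** SAP Section 5.2.2 does not say that SDUs are looked up by container. SAP Section 8 describes TLFB spreadsheets whose entries are checked for alcohol percentage, which is compatible with a volume-times-strength calculation. The row might then never be applied. Equally, no check of the volume-to-SDU factor is described, so the planned checks would not clearly catch the error.
- **Reach.** A reader might infer that every drinking endpoint is affected for all spirits drinkers. It is not: abstinence endpoints and full-pint heavy days do not move, and only spirits entered by the pint are concerned. Scaling the row to half a pint would give 4.25, below a man's heavy-day threshold of 5, but Table 2 has no half-pint row and the SAP states no such scaling rule. No effect on heavy-day status is claimed on that basis.
- **Bias.** The same table serves both arms, so a bias in favour of one arm is not expected.

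**Conclusion.** The inconsistency is established from the SAP's own figures: by its definition and its other spirits rows, 16 oz at 40% is 10.6 to 10.9 SDU, not 8.5.

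The effect on data is conditional. It arises only if 8.5 is applied to a true 16 oz, and then amounts to 2.2 SDU (20%) per pint. It reaches drinks per week, drinks per drinking day, men's very-heavy days, and WHO level and WHO decrease near cut-points. The primary VAS endpoint is untouched. The cost would be misclassification in secondary endpoints. Its effect on group estimates cannot be computed, because the number of pint reports is not stated, and it could be zero.

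The very-heavy flip rests on the stated 0.6 oz and 40%. If those approximate figures are varied over an assumed 0.55 to 0.65 oz and 38% to 42%, a 16 oz pint ranges from 16 × 0.38 / 0.65 = 9.35 to 16 × 0.42 / 0.55 = 12.22. That never reaches 8.5, though at the low end it would also fall below 10.

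**What to change.** Reconcile the row so that volume and value agree. Either set 16 oz to 10.7 SDU, or, if the smaller bottle was meant, relabel the row as about 12.75 oz (375 mL) at 8.5 SDU and add a row for 16 oz at 10.7.

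Then confirm which factor the TLFB spreadsheets use for spirits reported by the pint. If 8.5 was applied to 16 oz, recompute those entries, baseline included, and the endpoints derived from them.

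The cost is one table row and a check of the spreadsheet factor, plus recalculation of pint entries only if the check shows it is needed.

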**Table 2: Standard Drink Unit Definitions**

For Beer (~ 5% alcohol), the approximate number of SDUs in:

• 12 oz = 1.0

• 16 oz = 1.3

• 24 oz = 2.0

• 40 oz = 3.3

For malt liquor (~ 7% alcohol), the approximate number of SDUs in:

• 12 oz = 1.4

• 16 oz = 1.9

• 22 oz = 2.6

• 40 oz = 4.7

For table wine (~ 12% alcohol), the approximate number of SDUs in:

• 750 mL bottle = 25oz = 5.0

• 5 oz glass = 1.0

• 10 oz glass = 2.0

For 80 proof spirits (~ 40% alcohol), or hard liquor, the approximate number of SDUs in:

• 1.5 oz (mixed drink) = 1.0

• 16 oz (pint) = 8.5

• 25 oz (a fifth) = 17.0

• 1.75 L (59 oz) = 39.0

### **5.2.3. Very Heavy and Heavy Drinking Day**

A very heavy drinking day is defined as 8 or more drinks per day for a woman, and 10 or more for men. A heavy drinking day is defined as a day with 5 or more drinks (SDUs) for males and 4 or more drinks (SDUs) for females.

### **5.2.4. Days at Risk**

If a subject is being treated at an inpatient facility, is incarcerated, or otherwise under confinement, the days spent in under these conditions is considered a reduction in the days at risk for drinking and is deducted from the denominator in calculations of rates of drinking days.

### **5.2.5. Percentage of Subjects with No Heavy Drinking Days and Percentage of Subjects Abstinent from Alcohol**

The percentage of subjects with no heavy drinking days is the number of subjects that have no heavy drinking days during the period of interest divided by the number of subjects with at least one day of non-missing drinking data during the period of interest, multiplied by 100.

The percentage of subjects abstinent from alcohol is calculated similarly, except the numerator is the number of subjects that have no drinking days during the period of interest.

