Continuous secondary endpoints (percent heavy drinking days, percent very heavy drinking days, percent days abstinent, drinks per week, drinks per drinking day, number of cigarettes smoked per week, PACS, POMS, and PSQI score) during the last 4 weeks of treatment period will be analyzed using a mixed-effects model with site, assessment time, and baseline drinking as fixed factors. PROMIS will be analyzed with analysis of covariance model with baseline and treatment as factors. Models will also include time by treatment group interaction term. Additional covariates may be included that are significantly correlated with outcome and/or if there are differences across the treatment groups.

Analysis of the dichotomous secondary endpoints (percentage subjects with no heavy drinking days, percentage subjects abstinent from alcohol, percentage of subjects achieving at least a one and two-level shift in WHO alcohol consumption, and percentage of subjects with no nicotine use among subjects with any use during the week before randomization) during the last 4 weeks of treatment period will be conducted via logistic regression. Covariates may be included provided there are a sufficient number of events.

No imputation for missing endpoint data will be performed for secondary endpoints.

Safety Analyses: AEs will be coded using the most recent version of the Medical Dictionary of Regulatory Activities (MedDRA) preferred terms and will be grouped by system, organ, and class (SOC) designation. The severity, frequency, and relationship of AEs to investigational product will be presented by preferred term by SOC grouping. Listings of each individual AE including start date, stop date, severity, relationship, outcome, and duration will be provided. Each AE (based on preferred terminology) will be counted once only for a given

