a EOS - end of study. These assessments are to be done at Week 7 or if the subject discontinues early and agrees to a final clinic visit.

b Within each study week, there should be a least two days elapsed since the visit in the prior week.

- c Test for opiates (i.e., morphine test), cocaine, amphetamines, methamphetamine, THC, buprenorphine, methadone, benzodiazepines, oxycodone, barbiturates, 3,4-methylenedioxy-methamphetamine (MDMA – also known as ecstasy), and EtG.
- d Creatinine, urea nitrogen, total bilirubin, ALT, AST, alkaline phosphatase, GGT, albumin, total cholesterol, triglycerides, sodium, potassium, and chloride
- e Complete blood cell count including RBC, WBC, hemoglobin, hematocrit, and platelets.
- f A dipstick urinalysis will be performed that tests for specific gravity, ketones, pH, protein, blood, glucose, nitrites, bilirubin, and leukocyte esterase. If the dipstick is positive for blood, leukocyte esterase, or protein, then a microscopic analysis will be performed at the discretion of the investigator.
- g Sitting blood pressure and heart rate.
- h Telephone calls after the Week 1 and 2 in clinic visits will collect AEs, concomitant medications, CIWA-AR, and give a drug compliance reminder. The call during Week 2 should be several days before the cue session to remind the subject of the planned visit.
- i Two modules will be viewed this week.

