### **5.2. Alcohol Consumption Endpoints**

#### **5.2.1. Daily Quantity of Alcohol Consumption**

Drinking will be assessed using the TLFB methodology and Form 90 structured assessment pattern chart. The TLFB is a semi-structured interview that provides estimates of the daily quantity of alcohol consumption during specified time periods. It uses a calendar prompt and a number of other memory aids (e.g., holidays, payday, and other personally relevant dates) to facilitate accurate recall of drinking or other drug use during the target period. The procedure has been widely used in clinical and research contexts. It has demonstrated adequate levels of reliability and validity when administered as an in-person interview, over the telephone, and when administered via computer ([Carey-1997](#), [Sobell et al-1988](#), [Sobell et al-1996](#)).

If a subject is withdrawn from the study early and is no longer participating in clinic visits or providing TLFB drinking data but is willing to be contacted by phone at the week most proximal to dropout, then they will be asked about any drinking and heavy drinking during the time since last contact. Phone calls will continue until the end of the treatment period, as deemed acceptable by the patient. The two questions cover whether the subject had any heavy drinking days or drinking days during the period covered and will be used to capture drinking data in the absence of individual daily TLFB drinking data.

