### **5.2.6. Weekly Percentage of Heavy Drinking Days and Weekly Percentage of Days Abstinent**

Weekly percentage of heavy drinking days is the number of heavy drinking days in a 7-day period divided by 7 then multiplied by 100. The TLFB permits capturing data in a subsequent visit if a visit is missed; however, if fewer than 7 days are observed then the denominator is the number of days observed in the 7-day period. At least 3 days in a week must be observed; otherwise, the week is considered missing.

Weekly percentage of days abstinent is similarly calculated by using the number of days abstinent instead of the number of heavy drinking days.

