## **9.5. Handling of Missing Data**

The primary endpoint of craving cannot be imputed; likewise, for the other craving questions given during the human lab session. Secondary endpoints analyzed with mixed effects or logistic regression models are capable of handling missing data, so no imputation will be utilized. PROMIS scores are analyzed using ANCOVA which cannot handle missing data; therefore, only subjects with an assessment during the treatment period will be used and no imputation.

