**Listing 15: Brief Drinking Questionnaire – mITT Subjects**

Subject ID	Treatment Group	Date of Assessment	Date that the last day of non-missing drinking data was collected by TLFB	This is a period of XX days since the last day of drinking data that was collected by TLFB	Did the subject drink during this period?	How many days during this period did the subject drink?
xxx	ASP8062	ddmmmyyyy	ddmmmyyyy	xx	Yes	xx
	Placebo				No	

Subject ID	Treatment Group	Date of Assessment	How many alcoholic drinks on a typical day?	How many heavy drinking days?	Maximum number of drinks on any one day?	How many days did you drink this maximum number?
xxx	ASP8062	ddmmmyyyy	xx	xx	xx	xx
	Placebo					

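### One observed event-free day in Weeks 3-6 is enough to score a subject as abstinent, or free of heavy drinking, for the full four weeks

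*SAP*

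**What the plan says.** SAP 5.2.5 defines the percentage of subjects with no heavy drinking days as those with no such day in the period, "divided by the number of subjects with at least one day of non-missing drinking data during the period of interest". Percentage abstinent is built the same way. SAP 9.4.3 sets the period as Weeks 3 through 6, which is Days 15 to 42.

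On missing data, the protocol synopsis states: "No imputation for missing endpoint data will be performed for secondary endpoints". SAP 9.5 gives a reason: "Secondary endpoints analyzed with mixed effects or logistic regression models are capable of handling missing data, so no imputation will be utilized".

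Neighbouring definitions do set minimums. SAP 5.2.6 and 5.2.7 need 3 observed days in a week. SAP 5.2.8 needs 1 week of data in the four-week window for the WHO responder endpoints.

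Four provisions limit the loss of drinking data:
- SAP 4 admits to the mITT set only subjects with the primary craving score, collected at the Week 3 visit.
- SAP 5.2.1 provides two telephone questions, on any drinking and any heavy drinking, for subjects who stop giving timeline follow-back (TLFB) data. The answers "will be used to capture drinking data in the absence of individual daily TLFB drinking data", and Listing 15 records the period covered ("This is a period of XX days since the last day of drinking data that was collected by TLFB").
- The end-of-study assessments include TLFB, and footnote a of the Schedule of Assessments offers them to early leavers: "These assessments are to be done at Week 7 or if the subject discontinues early and agrees to a final clinic visit".
- SAP 5.2.6 notes that "The TLFB permits capturing data in a subsequent visit if a visit is missed".

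**The concern.** A clean partial record is scored as a clean four weeks. A subject last seen in Week 3 with two clean days carries the same weight as one with 28 clean days, and nothing later in the plan corrects this.

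The reason given in SAP 9.5 does not help. Each subject enters the logistic model as one derived yes or no, so the missing days have already become an observed success before the model is fitted.

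The recovery routes depend on the subject. The final visit needs agreement, back-capture needs a return visit, and on the telephone questions the SAP says: "Phone calls will continue until the end of the treatment period, as deemed acceptable by the patient". SAP 5.2.5 also does not say how a telephone answer enters the count. At stake are the two reported rates and, if loss differs between arms in amount or timing, the comparison between them.

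**Working it through.** **No stated figure to reproduce.** The documents give no dropout rate, responder rate or power for these two endpoints.

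**Direction.** No event on 28 days implies no event on the observed days, but not the reverse. Among subjects in the denominator, missing days can therefore only leave a rate unchanged or raise it. A subject with 0 observed days leaves the denominator.

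**Days observed, by last visit attended.** Visit windows are from the Schedule of Assessments. I assume TLFB runs to the day before the visit, which the SAP does not state.
- Week 3 (Days 15-21): 0-6 of 28 days
- Week 4 (Days 22-28): 7-13
- Week 5 (Days 29-35): 14-20

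**Against the SAP's own minimum.** A subject with 1-6 clean days falls short of the 1 week needed for the WHO endpoints, yet is a success here. This takes the WHO window as Weeks 3-6, as in SAP 9.4.3 and Tables 70, 72 and 73. SAP 5.2.8 and 9.4.3.1 say Weeks 2-5, and on that window Week 2 would supply the missing week.

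**A simple count (assumed).** Take 30 subjects in an arm: 26 complete with 4 successes, and 4 lost with 1-6 clean days.
- As written: 8/30 = 26.7%
- With a 1-week minimum: 4/26 = 15.4%
- Lost counted as non-success: 4/30 = 13.3%

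**Model for no heavy drinking days (all inputs assumed).** 12% never drink heavily. The rest have a daily heavy-drinking probability from Beta(2,3), so P(no heavy day in n days) = 12/((n+3)(n+4)). Visit days are uniform within each week.
- The mean of this probability is 0.300 for n = 1-6, 0.0706 for n = 7-13 and 0.0294 for n = 14-20. At n = 28 it is 0.0121.
- True rate: 0.12 + 0.88 × 0.0121 = 13.1%.
- Scored success by last visit: Week 3, 0.12 + 0.88 × 0.300 = 38.4%; Week 4, 18.2%; Week 5, 14.6%.
- Arm rate with 20% lost, all after Week 3 (1 in 7 of them has 0 days): [0.80 × 0.1306 + 0.20 × (6/7) × 0.384] / [0.80 + 0.20 × (6/7)] = 17.5%. With 5% lost: 14.2%.

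| Scenario, no drug effect unless stated | Reported rates | False difference, points |
|---|---|---|
| 20% vs 5% lost, all after Week 3 | 17.5% vs 14.2% | +3.4 |
| 20% vs 5%, spread evenly over Weeks 3, 4, 5 | 15.0% vs 13.5% | +1.4 |
| 20% in both arms, same timing | equal | 0 |
| 20% in both, one arm after Week 3, the other after Week 5 | 17.5% vs 13.4% | 4.2 |
| 20% after Week 5 vs 5% after Week 3 | 13.4% vs 14.2% | 0.8, favouring the arm with less loss |
| Real effect (25% vs 12% never heavy), 20% in both after Week 3 | 29.7% vs 17.5% | true 12.8 reported as 12.2 |

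Other checks at 20% vs 5%, all after Week 3 / evenly spread:
- Half the losses recovered: 1.7 / 0.7.
- 10% vs 5% loss instead: 1.1 / 0.5.
- Other assumed drinking distributions: 2.5-5.1 / 1.0-2.7.
- Abstinence (5-12% never drinking, the rest Beta(4,2)): 1.2-1.3 / 0.4-0.5.

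**Standard error at 30 per arm.** √(0.175 × 0.825/30 + 0.142 × 0.858/30) = 9.4 points; 9.0 for the even spread.

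**Alternatives on the same model.** Bias in the difference at 20% vs 5%, all after Week 3 / evenly spread:

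| Rule | Loss unrelated to drinking | Every lost subject truly a failure |
|---|---|---|
| Current 5.2.5 | +3.4 / +1.4 | +4.2 / +1.8 |
| Only subjects with enough observed days | 0 / 0 | +2.6 / +2.6 |
| Incomplete event-free subjects as non-success | -2.0 / -2.0 | 0 / 0 |

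**The case against.** The strongest reply is that the plan already handles most of this. The telephone questions ask exactly what these endpoints need. Table 14 reports dropouts, and Table 15 the use of those questions, by week and arm, so a reader can see unequal loss. Subjects lost before the cue session are outside mITT. Every input to the sizes above is assumed, and the results are small against the standard error.

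Much of this stands, and it sets the severity. It does not remove the point. The routes are voluntary, and neither table counts the subjects scored as successes on incomplete records.

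It is also fair to say that no single replacement rule is clearly better. A reader might infer that the cure is to analyse only well-covered subjects. The last table above does not support that as a correction: with evenly spread losses its worst bias over the two cases is 2.6 points, against 1.8 for the current rule. It would also discard subjects whose recorded heavy day already settles the endpoint.

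**Conclusion.** The point holds as a minor one. SAP 5.2.5 can score a few clean days as 28, no other rule corrects it, and the statement in SAP 9.5 about logistic regression is wrong for these endpoints. Two of 15 secondary endpoints are affected; the primary is not.

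The false difference is roughly 0.5 to 4 points in most scenarios, on assumed drinking and loss rates, and is unlikely to decide a result.

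Two stronger readings are tempting. One is that the bias always favours the arm with more loss; the Week 5 against Week 3 scenario shows the reverse. The other is that equal loss makes the comparison safe. That needs the same timing in both arms and no drug effect: equal loss at different times gave 4.2 points, and a real effect shrank from 12.8 to 12.2. Since the documents state no loss rates or timing, neither the direction nor the size can be fixed in advance.

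**What to change.** 1. **SAP 5.2.5.** State that periods answered by the brief questions of 5.2.1 count as observed, and that any heavy drinking (or, for abstinence, any drinking) reported in them is a non-success.
2. **Sensitivity analysis, specified before unblinding.** Use the full mITT set. Recorded heavy (or drinking) days stay failures, and event-free subjects with incomplete coverage count as non-successes. Label this a lower bound for each arm's rate, with a one-line exception to the no-imputation rule. Label the current rule an upper bound among subjects with at least one observed day. These bound each arm's rate, not the difference, so claim an effect only if its direction holds under both. Report the number of under-covered event-free subjects by arm.
3. **Optional minimum-data rule.** If the sponsor wants one, it should be at least the 1 week of SAP 5.2.8, set as an absolute number of observed days. A share of days at risk (5.2.4) would let a subject confined for 26 of 28 days qualify with 2. The threshold, and any analysis of covered subjects only, are the sponsor's choice.
4. **SAP 9.5.** Remove the claim that logistic regression handles missing data for these endpoints.
5. **Model for percentage abstinent.** SAP 9.4.3.1 assigns it to the mixed model; the protocol synopsis and Table 69 use logistic regression. Reconcile them.

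The cost is SAP wording and one extra analysis, with no new data. The downside to state is that the lower bound is biased against the arm with more loss when loss is unrelated to drinking (about 2 points at 20% vs 5%).
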